Cardiopulmonary exercise testing (CPET): Exercise tests will be conducted on an electronically-braked cycle ergometer (Ergometrics 800S; SensorMedics) using a SensorMedics Vmax229d system as previously described (34-36). Incremental CPET will consist of steady-state rest followed by 1 minute of warm-up of unloaded pedalling then 10 watt increases in work rate every minute to the point of symptom-limitation [Appendix 5]. Maximal work rate (Wmax) will be defined as the highest work rate the subject can maintain for at least 30 seconds. Constant-load tests will consist of steady-state rest, 1 minute of warm-up of unloaded pedalling and then an immediate stepwise increase work rate to 75% which will be maintained for 4 minutes (see below). Measurements will include: standard cardiorespiratory and breathing pattern parameters collected on a breath-by-breath basis and compared with predicted values based on age and height (65); oxygen saturation by pulse oximetry; heart rate by 12-lead ECG; blood pressure by auscultation; operating lung volumes derived from IC maneuvers (66,67); EMGdi-derived measures of inspiratory neural drive to the diaphragm; the intensity of perceived leg discomfort; and exertional dyspnea intensity, quality and unpleasantness. Three main time points will also be evaluated: rest will be defined as the steady-state period after at least 3 minutes of breathing on the mouthpiece before exercise starts (cardiopulmonary parameters will be averaged over the last 30-sec of this period and resting ICs will be collected while breathing on the same circuit immediately after completion of the quiet breathing period); isotime will be defined as the last 30-sec increment of each minute (i.e., 1-min, 2-min, 3-min) during the 4-min exercise tests, and; end-exercise will be defined as the last 30-sec of loaded pedaling (i.e., 4-min).

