Respiratory pressures and diaphragm electromyography (EMGdi). An esophageal electrodeballoon catheter will be inserted nasally and positioned as previously described (30,71). EMGdi will be recorded continuously using an esophageal electrode catheter consisting of 5 electrode pairs at rest and during exercise and analyzed as previously described (34-36). The raw EMGdi signal will be sampled at 2000 Hz (PowerLab, model ML880; ADInstruments, CastleHill, NSW, Australia), band-pass filtered between 20-1000 Hz (Bioamplifier model RA-8; Guanzhou Yinghui Medical Equipment Co. Ltd. Guangzhou, China) and converted to a root mean square (RMS) using computer software (Chart v5.4, ADInstruments). For each breath, the data from the electrode pair with the largest value from the five electrode pairs will be used for analysis. Maximal EMGdi (EMGdi,max) will be determined from IC maneuvers (72). EMGdi/EMGdi, max will be used as an index of the inspiratory neural drive to the crural diaphragm (30-33). Esophageal (Pes) and gastric pressures (Pga) will be recorded continuously at a rate of 200 Hz (PowerLab); transdiaphragmatic pressure (Pdi) will be recorded as the difference between Pga and Pes signals. The continuous flow signal from the Vmax229d system will be input into the PowerLab system for offline analysis. Pre- and post-exercise inspiratory sniffs will be performed to obtain maximum Pes (Pes,sn) and Pdi (Pdi,sn). IC maneuvers at rest and throughout exercise will be used to obtain dynamic peak inspiratory Pes (Pes,IC) and Pdi (Pdi,IC). Pre- and post-exercise FVC maneuvers will also performed to obtain dynamic peak expiratory Pes (Pes,FVC). Respiratory mechanics will be analyzed as previously described (34-36).

Statistical analysis: A sample size of 17 will provide at least 80% power to detect a clinically significant treatment difference of 1 Borg unit in dyspnea intensity at a standardized time during constant work-rate exercise (i.e., at the end of the 4-min exercise test). This sample size estimation is based on the following assumptions: a standard deviation of 1.35 Borg units for the difference between values in a two-treatment crossover study [Appendix 3] (37,40), α =0.05, β =0.8, and a two-tailed test of significance. A p<0.05 significance level will be used for all statistical analyses.

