Paired *t*-tests with appropriate Bonferroni adjustments for multiple comparisons will be used to compare treatment responses, i.e., post-dose responses to fentanyl citrate versus bronchodilator. Comparisons will be made for: 1) resting pulmonary function; 2) cardiorespiratory (e.g., V_E, V_T, breathing frequency, HR, etc.), respiratory mechanical (e.g., IC, inspiratory reserve volume (IRV)), metabolic and gas exchange (e.g., VO₂, carbon dioxide output (VCO₂), end-tidal CO₂ (P_{ET}CO₂), SpO₂), and perceptual (e.g., intensity of dyspnea and leg discomfort) responses measured at rest, isotime and end-exercise; 3) Pes, Pga and Pdi-derived measurements of respiratory mechanics and muscle recruitment patterns; 4) EMGdi-derived indices of inspiratory neural drive (e.g., EMGdi/EMGdi,max). Descriptors of dyspnea at end-exercise and reasons for stopping exercise will be analyzed as frequency statistics and compared between-groups and between-treatments using Fisher's exact test.

To identify contributors to exertional dyspnea intensity (and its qualitative and affective dimensions), Pearson correlations will be used to establish associations between intra-subject treatment differences (i.e., post- minus pre-treatment) in isotime (4-min) measurements of exertional dyspnea intensity and relevant independent variables which will include: concurrent differences in cardiorespiratory and dynamic respiratory mechanical measurements at isotime during exercise; differences in resting lung function measurements, and; various baseline characteristics (possible

covariates). A multivariable linear regression model will be used to further evaluate the relationship between dyspnea intensity and any significant variables: treatment will be included as a categorical effect, an interaction term will be used to determine whether the relationship was similar across treatments (independent variable*treatment), and subjects will be treated as random effects to account for serial measurements (subject nested within treatment).

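### Bonferroni is valid for the paired t-tests, but Holm's step-down procedure holds the same 5% family-wise error and is never less powerful; the gain is modest and depends on how many effects are real

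*Combined protocol and SAP*

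**What the plan says.** The Statistical analysis section plans paired t-tests of post-dose fentanyl against post-dose bronchodilator, "with appropriate Bonferroni adjustments for multiple comparisons will be used to compare treatment responses". The list covers resting pulmonary function, then cardiorespiratory, mechanical, gas-exchange and perceptual "responses measured at rest, isotime and end-exercise", then pressure-derived measures and EMGdi indices. Time points are not restated for the last two groups.

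The exercise testing section gives the time points: "isotime will be defined as the last 30-sec increment of each minute (i.e., 1-min, 2-min, 3-min) during the 4-min exercise tests", with end-exercise at 4 min. Counting rest, that is up to five comparisons per exercise variable.

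The plan names no step-down method and states neither the family nor the number of tests. Dyspnea intensity appears in the adjusted list. It is also the variable behind the primary endpoint (Appendix 4, change at 4 min) and the sample size. That calculation uses an unadjusted 0.05, and the section adds that "A p<0.05 significance level will be used for all statistical analyses".

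**The concern.** Bonferroni compares every p-value with 0.05/m, where m is the number of tests in the family. Holm does so only for the smallest p-value. It then uses 0.05/(m-1), 0.05/(m-2) and so on, and stops at the first failure. It needs no further assumption, holds the same family-wise error, and cannot reject less. When two procedures give the same guarantee from the same p-values, there is little reason to specify the weaker one.

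The comparisons matter because the hypothesis is about mechanism: inspiratory neural drive, mechanics and their relation to dyspnea. With 17 patients there is little power to spare. What is at stake is how many time points of an outcome can be declared different, and so how fully its course over exercise can be described.

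**Working it through.** **Inputs from the plan.** n = 17 ("A sample size of 17 will provide at least 80% power"); a difference of 1 Borg unit ("to detect a clinically significant treatment difference of 1 Borg unit in dyspnea intensity"); "a standard deviation of 1.35 Borg units for the difference between values in a two-treatment crossover study"; alpha 0.05 with "a two-tailed test of significance".

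**Assumed, not in the plan.** One family per outcome with m = 5 (rest, 1, 2, 3, 4 min). Standardised effect 1/1.35 = 0.74, borrowed from dyspnea, with 0.5 as a sensitivity value. Equal correlation of 0.5 or 0.8 between time points. One to five of the effects real.

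**Step 1: the plan's own figure.** Paired t-test power comes from the noncentral t distribution with n-1 degrees of freedom and noncentrality √n × 1/1.35. For n = 17 this is √17 × 0.741 = 3.05. Power is 79.1% at n = 16 and 81.8% at n = 17, so 17 is reproduced.

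**Step 2: power of one test at each Holm threshold (m = 5, 0.74 SD).**

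| Step | Threshold | Power |
|---|---|---|
| 1 (also Bonferroni) | 0.05/5 = 0.0100 | 56.4% |
| 2 | 0.05/4 = 0.0125 | 60.2% |
| 3 | 0.05/3 = 0.0167 | 65.0% |
| 4 | 0.05/2 = 0.0250 | 71.6% |
| 5 | 0.05/1 = 0.0500 | 81.8% |

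The span from first to last step, about 25 points, is a ceiling for a single time point. It is reached only if the other four are practically certain to be rejected.

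**Step 3: realistic gain.** Simulation of 40,000 trials per row and correlation, n = 17, m = 5, average power per true effect:

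| Real effects | Bonferroni | Holm, corr. 0.5 | Holm, corr. 0.8 | Gain (points) |
|---|---|---|---|---|
| 5 of 5, 0.74 SD | 56% | 69% | 67% | 10-12 |
| 4 of 5 | 56% | 64% | 63% | 7-8 |
| 3 of 5 | 56% | 61% | 60% | 4-5 |
| 2 of 5 | 56% | 58% | 58% | 2 |
| 1 of 5 | 56% | 56% | 56% | 0 |
| 5 of 5, 0.5 SD | 23% | 29% | 30% | 6 |

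**Step 4: what does not change.** Holm's first threshold is the Bonferroni threshold, so the chance of rejecting at least one time point is identical. With all five real at 0.74 SD it is 89% at correlation 0.5 and 78% at 0.8 under both methods.

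**Step 5: error.** With no real effects, the chance of any false positive is 4.4% (correlation 0.5) or 3.2% (0.8) under both methods. With four of five real, it rises from about 1% to about 3% for the remaining null, inside the 5% bound.

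**The case against.** Bonferroni is valid and conservative, so preferring Holm is a matter of efficiency. That stands, and it sets the severity. Several stronger readings are tempting, and the documents do not support them.

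- *A gain of about 17 points.* A reader can reach this with 20 tests, 0.9 SD and every effect real (57% to 74%). The plan contains neither figure, and a five-test family does not give that average gain at 0.74 SD.
- *All five effects real.* The contrast is fentanyl against bronchodilator, and the hypothesis expects neural drive to fall with both. The EMGdi difference could be small or nil, and a difference at rest is not the focus. The lower rows of the table may be nearer the truth.
- *Bonferroni could hide an outcome's effect altogether, and Holm would recover it.* It would not, by Step 4.
- *Correlated measurements call for Holm.* Holm ignores correlation. With all five effects real, the gain falls from about 12 points at correlation 0.5 to about 10 at 0.8.
- *The change is free.* There is no loss of power or of the 5% guarantee, but Holm has no simple matching simultaneous intervals, and more of the 5% is used when some effects are null.
- *The mechanism conclusion rests on these tests.* Only in part: the plan also has correlations of within-subject changes and a regression with a treatment interaction, which the Bonferroni sentence does not govern.

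It can also be said that the undefined family is the larger gap. That is fair: neither method can be applied until the family is fixed, so the fix must define it.

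**Conclusion.** The point holds as an efficiency improvement. For the same family-wise error, Holm gives about 10-12 points more power per true effect in a five-test family if all effects are 0.74 SD and real, falling to none if only one is real, and about 6 points if all five are 0.5 SD. These sizes rest on a borrowed effect size, an assumed family of five and equal correlation. That Holm never rejects less than Bonferroni rests on none of these. The choice changes how many time points are declared significant for an outcome that already shows one; it does not change which outcomes show any. Low severity.

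**What to change.** Replace the Bonferroni wording with:

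> The primary comparison (dyspnea intensity at 4 min) is tested at two-sided 0.05 outside these families, as assumed in the sample size. For every other outcome measured during exercise, the comparisons at rest, 1, 2, 3 and 4 min form one family (for dyspnea intensity, the remaining time points). The resting pulmonary function variables form one family. Each family is adjusted by the Holm step-down procedure (two-sided family-wise 5%). Adjusted p-values are reported, with unadjusted 95% confidence intervals labelled as such.

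The first sentence is needed because a rule applied to every outcome would otherwise put the primary test in a family of five, where Bonferroni power is 56% and not the planned 80%. Families set per outcome do not control error across outcomes, and the report should say so.

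The cost is a short paragraph of text and one line of code, with no extra patients or measurements. The drawbacks are the lack of simple simultaneous intervals and a false-positive chance nearer to 5%, though within it, when some effects are null.

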Study design: This will be a single-centre, randomized, double-blind, 2-treatment crossover study evaluating the differential effects of nebulized fentanyl citrate (100µg) and nebulized bronchodilator (0.5mg ipratropium bromide + 2.5mg salbutamol) on exertional dyspnea and physiological responses to a standardized exercise task. After giving written informed consent, participants will complete 5 visits, each conducted in the morning 2-7 days apart [Appendix 4]. Visit 1 (screening): medical history, symptom evaluation, complete pulmonary function testing, a symptom-limited incremental exercise test to determine maximal work rate (Wmax), and familiarization to a new standardized exercise task (4-min cycle exercise test). Visits 2 & 3 (run-in): repeatability of the 4-min cycle exercise test. Visits 4 and 5 (treatment): pre-drug pulmonary function tests (spirometry, plethysmography) and a 4-min cycle exercise test while breathing a gas mixture with a constant fraction of 21% oxygen (room air = 21%) FiO₂); nebulized of either fentanyl or bronchodilator; 30-min post-drug, subjects will perform post-drug pulmonary function tests and a 4-min cycle exercise test while breathing a gas mixture with a constant fraction of 30% oxygen (30% FiO₂) after fentanyl and 21% oxygen (21% FiO₂) after bronchodilator. Exercise tests at Visits 4 and 5 will include detailed measurements of dyspnea (intensity, quality, affective dimensions), EMGdi and pressure-derived respiratory mechanical measurements. Vital signs and systemic side-effects will be monitored. Regularly used inhaled corticosteroids will be permitted as usual throughout the study. Subjects will adhere to the standard withdrawal of bronchodilators prior to each visit: short-acting β_2 -agonists, short-acting anticholinergies, long-acting β_2 -agonists and long-acting anticholinergics will be withdrawn 6, 12, 24 and 24 hours, respectively. Subjects will avoid caffeine, heavy meals, alcohol and major physical exertion prior to visits. Although inhalation of fentanyl citrate has not been associated with significant adverse symptoms or side-effects there is always a possibility that study participants could experience certain side-effects such as drowsiness, sedation and dizziness. As such, participants will be required to have someone accompany them home after their fourth and fifth study visit. If someone is not available to drive them on those days they will be required to take a taxi to and from the lab.

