APPENDIX 3 Exertional Dyspnea Intensity in Response to Bronchodilators and Opiates

Dyspnea-ventilation relationships during constant-work rate exercise in COPD are shown from two different randomized, placebo-controlled crossover studies performed at the Respiratory Investigation Unit. **Bronchodilators** (*left*): In response to nebulized bronchodilator (ipratropium 0.5mg + salbutamol 2.5mg), dyspnea fell significantly for a given ventilation in 16 patients with moderate-to-severe COPD [Peters M, et al. Thorax 2006;61:559-567]. Reductions in dyspnea intensity were attributed to improvements in respiratory mechanics (i.e., an increased inspiratory capacity allowed greater tidal volume expansion). Opiates (right): In response to nebulized fentanyl 50µg (right), dyspnea-ventilation relationships were unaltered in 12 patients with COPD [Jensen D, et al. J Pain Symptom Manage 2012;43:706-719]. Decreases in ventilation with inhaled fentanyl resulted from decreases in breathing frequency (prolongation of expiratory time), with little change in respiratory mechanical measurements.

Hypotheses: The relationship between dyspnea intensity and inspiratory neural drive to the diaphragm (EMGdi/EMGdi,max) will remain constant across both interventions (compared with placebo or pre-treatment conditions). Therefore: 1) improved respiratory mechanical/muscle function after a bronchodilator will necessitate lower inspiratory neural drive for a given ventilation; and 2) a reduction in inspiratory neural drive after fentanyl will result in a proportional decrease in ventilation. A schematic illustration of these responses is shown below.

[figure not shown]

APPENDIX 4

Study Design

Two-treatment crossover study (Fentanyl, Bronchodilator)

Experimental visits

Pre-treatment: Insertion of EMGdi-pressure catheter PFTs (spirometry, body plethysmography) Constant work rate exercise (4-min exercise test) breathing 21% oxygen Treatment: Primary endpoint: 15-min nebulization of either fentanyl or bronchodilator ΔDyspnea at 4-min of exercise 30-min rest Post-treatment: PFTs (spirometry, body plethysmography) Constant work rate exercise (4-min exercise test) breathing either 30% oxygen (Fentanyl) or 21% oxygen (bronchodilator)

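### The treatment comparison uses post-dose values only and leaves out the same-visit pre-drug test, and the delta in the Appendix 4 primary endpoint is undefined: a matter of precision, not of bias or a power shortfall

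*Combined protocol and SAP*

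**What the plan says.** Under Study design, Visits 4 and 5 each begin with "pre-drug pulmonary function tests (spirometry, plethysmography) and a 4-min cycle exercise test" on 21% oxygen. Nebulization follows, then lung function and a second 4-minute test. Visits are on separate mornings 2 to 7 days apart. Appendix 4 lists the pre-treatment block as "Insertion of EMGdi-pressure catheter PFTs (spirometry, body plethysmography) Constant work rate exercise (4-min exercise test) breathing 21% oxygen", so the pre-drug and post-drug tests of one visit share one catheter insertion.

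Under Statistical analysis, paired t-tests with Bonferroni adjustments "will be used to compare treatment responses, i.e., post-dose responses to fentanyl citrate versus bronchodilator". This covers resting lung function, cardiorespiratory and perceptual responses, pressure-derived measures and EMGdi indices. The comparison has no baseline term. Post-minus-pre differences appear only in the Pearson correlations that follow. The regression after those names treatment, an interaction and subject effects, but not the pre-drug value of the outcome.

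Appendix 4 labels the primary endpoint as a delta in dyspnea at 4 minutes of exercise. It does not say whether delta means post minus pre or fentanyl minus bronchodilator.

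On size, the plan states: "A sample size of 17 will provide at least 80% power to detect a clinically significant treatment difference of 1 Borg unit in dyspnea intensity", assuming "a standard deviation of 1.35 Borg units for the difference between values in a two-treatment crossover study".

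**The concern.** The two post-dose values that the t-test compares come from different mornings. Whatever shifts a patient's level on a given day enters the treatment difference as noise. The pre-drug test at the same visit measures that shift under conditions that are the same for both treatments, before the drug of that day is given. It is therefore a legitimate covariate, and it is already being collected.

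For dyspnea the issue is day-to-day variation only. EMGdi and pressure measures may carry a further component, because each visit has its own catheter insertion.

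The undefined delta adds a second problem. If it is post minus pre, the plan contains two different primary analyses, and the change score can be clearly less precise than the t-test on post-dose values. Unless one is named, the choice between post-dose, change-score and adjusted analyses stays open after the data are seen.

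**Working it through.** **Inputs from the Statistical analysis section.** n = 17; SD of the difference 1.35 Borg; effect 1 Borg at the end of the 4-minute test; alpha 0.05; "a two-tailed test of significance".

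**Assumptions not in the documents.** The SD of 1.35 is taken as the SD of the post-dose difference between visits; the plan does not say which difference it describes. The pre-drug difference is given the same SD. The correlation r is varied over a range.

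**Step 1: the plan's own figure.** SE = 1.35/√17 = 0.327. Noncentrality = 1/0.327 = 3.05, with 16 df. Noncentral t power is 81.8%; n = 16 gives 79.1%. So 17 is the smallest sample size reaching 80%, and the plan's figure reproduces.

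**Step 2: what r is.** Write each measurement as patient + visit + test error, with visit variance V and test variance E.

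- The post-dose difference between visits has variance 2(V + E), so all visit variation is in the error.
- The pre-drug difference has the same variance, and its covariance with the post-dose difference is 2V.
- Hence r = V/(V + E): the correlation between the two between-visit differences, after stable patient differences have cancelled.
- It is not the correlation between a patient's values at two visits. Drug response that varies between patients would lower it.

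**Step 3: the three analyses.**

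- Post-dose only: SD 1.35 at any r, 16 df.
- Change score: SD = 1.35 × √(2(1 − r)), 16 df. This equals 1.35 at r = 0.5 and is larger below that.
- Adjusted: residual SD = 1.35 × √(1 − r²), 15 df, with the variance inflated by 1 + 1/(n − 4) = 1 + 1/13 for estimating the slope.

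| r | Post-dose only, power | Change score, SD / power | Adjusted, residual SD / power |
|---|---|---|---|
| 0 | 81.8% | 1.91 / 52.8% | 1.35 / 78.5% |
| 0.3 | 81.8% | 1.60 / 67.9% | 1.29 / 82.2% |
| 0.5 | 81.8% | 1.35 / 81.8% | 1.17 / 88.8% |
| 0.7 | 81.8% | 1.05 / 95.9% | 0.96 / 97.0% |

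At r = 0.5 the adjusted SE is 1.17 × √(1 + 1/13)/√17 = 0.29, against 0.33 for post-dose only. At r = 0 the adjustment costs 81.8 − 78.5 = 3.3 points by this approximation. Averaging over the chance spread of the covariate instead gives 79% at r = 0, a loss of about 3 points, and puts break-even with the planned test near r = 0.27.

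**Step 4: chance imbalance.** With equal SDs, the regression of the post-dose difference on the pre-drug difference has slope r. If the mean pre-drug values at the two visits differ by chance by d, the unadjusted estimate is expected to shift by about r × d, not by d.

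**The case against.** The strongest reply is that nothing is broken. The planned test meets its stated 80% power. If 1.35 came from post-dose differences in the earlier crossover studies, it already includes day-to-day noise. Randomized order protects against bias. All of this stands. A reader might infer that the trial is underpowered or that the comparison is biased; the documents support neither.

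A second reply is that the gain is not guaranteed. Below r of about 0.27 the adjusted analysis has slightly less power than the plan, and at 0.3 the gain is under one point. The stability criterion, the familiarization test and the run-in visits are meant to limit visit-level variation, which would keep r low. This also stands. The Visit 2 and 3 repeatability data will show the total between-visit variation but not r, which needs pre-drug and post-dose pairs.

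Third, one might infer that catheter position contaminates every outcome. It has no stated route to dyspnea ratings. For EMGdi, the plan takes the largest of five electrode pairs at each breath and scales to a maximum from IC maneuvers, which removes part of any insertion effect. How much remains cannot be computed from the documents, so no size can be put on the EMGdi or pressure component.

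Fourth, the delta in Appendix 4 may already mean post minus pre, in which case the baseline would be used for dyspnea. It may, but the analysis text spells out treatment responses as post-dose responses, so that reading produces a contradiction. Nor can one infer that the pre-drug test is wasted: it feeds the correlation analyses. The gap is confined to the treatment comparison.

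**Conclusion.** The point holds as one of efficiency and specification. The treatment comparison, as written, leaves day-to-day variation in the error for all outcomes. For EMGdi and pressure measures it also leaves whatever insertion variation scaling does not remove. Separately, the primary endpoint label in Appendix 4 is undefined and may conflict with the Statistical analysis section.

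The size depends on r: from a loss of about 3 power points at r = 0, through no change near 0.27, to a gain of about 7 points at 0.5 and 15 at 0.7. This rests on 1.35 being the SD of the post-dose difference and on equal SDs before and after dosing. A plain change score is not a safe substitute, because it loses power against the planned test whenever r is below 0.5. The change is worth making because its downside is small and bounded, not because a large gain is certain.

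**What to change.** 1. Define the primary endpoint in the same terms in the Statistical analysis section and in Appendix 4, stating what delta means.
2. Replace the paired t-test sentence with wording such as: each treatment comparison will regress the within-patient difference in post-dose values (fentanyl visit minus bronchodilator visit) on the corresponding difference in same-visit pre-drug values; the intercept is the treatment effect, reported with a 95% confidence interval; the Bonferroni adjustments are kept.
3. Apply this to 4-minute dyspnea, EMGdi/EMGdi,max, pressure-derived measures, operating lung volumes, ventilation and resting lung function.

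The cost is wording, one degree of freedom, and up to about 3 power points if r is near zero. No new measurement is needed. The change should be made before treatment codes are released, so that the choice of analysis does not depend on the results.

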Adjustment of work rate for 4-min cycle tests. The work rate during the constant-load test will be adjusted to the highest work rate that can be sustained for the entire 4 minutes; the objective is to induce a level of dyspnea (a modified Borg rating \geq 3) that is sufficiently high to be amenable to therapy. After completion of the incremental test and an adequate rest period at Visit 1, a 4-minute cycle test at 75%Wmax will be conducted. If the subject can complete 4 minutes and reaches a dyspnea intensity \geq 3 Borg units, then these work rate settings will be used for all subsequent cycle tests. If the subject cannot complete 4-minutes, then a lower work-rate (60%) will be tested. If the subject completes the 4-minutes but does not reach a high enough dyspnea rating, then a higher work-rate (90%) will be tested. At run-in Visit 2, further refinement of work rate will be conducted if required. After final selection of work rate to use for 4-min tests, repeatability of tests conducted at Visits 2 and 3 using the final selection of work rate will be evaluated by comparing end-exercise dyspnea intensity ratings and standard cardiopulmonary measurements.

Symptom evaluation. Dyspnea (respiratory discomfort) will be defined as the "sensation of breathing discomfort" and leg discomfort as "the sensation of leg discomfort experienced during pedalling." The intensity (strength) of sensations will be rated at rest and during exercise using the modified 10-point Borg scale (68). We have recently provided validation for the novel use of the same

scale for measuring the intensity of several descriptive phrases related to specific qualities of dyspnea (e.g., effort, unsatisfied inspiration) and the affective dimension (e.g., unpleasantness) of dyspnea (37,69,70). This will allow us to assess which component(s) of perceived dyspnea is modified by the active intervention. Upon exercise cessation, subjects will be asked to verbalize their main reason for stopping exercise, i.e., breathing discomfort, leg discomfort, their combination or some other reason. Qualitative descriptors of respiratory discomfort at end-exercise will be collected by questionnaire (19).

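### Reasons for stopping exercise are compared between treatments, but the post-drug test is a fixed 4-minute bout, so only tests that end early say anything about exercise limitation

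*Combined protocol and SAP*

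**What the plan says.** All references are to METHODS in the combined protocol and SAP unless stated otherwise.

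- *Statistical analysis*: "Descriptors of dyspnea at end-exercise and reasons for stopping exercise will be analyzed as frequency statistics and compared between-groups and between-treatments", with Fisher's exact test named as the method.
- *Symptom evaluation*: when exercise ends, "subjects will be asked to verbalize their main reason for stopping exercise". The reasons foreseen are breathing, legs, both together, or something else. No category is given for reaching the planned end of the test.
- *Study design*: after each drug, "subjects will perform post-drug pulmonary function tests and a 4-min cycle exercise test". Appendix 4 shows the same schedule.
- *Cardiopulmonary exercise testing*: the constant-load test is an "immediate stepwise increase work rate to 75% which will be maintained for 4 minutes". The end-exercise time point is equated with 4 minutes.
- *Adjustment of work rate for 4-min cycle tests*: the load is "adjusted to the highest work rate that can be sustained for the entire 4 minutes". For non-completion the rule is: "If the subject cannot complete 4-minutes, then a lower work-rate (60%) will be tested". A higher load (90%) is tried if the patient finishes with too little dyspnea. Further refinement is allowed at Visit 2, and repeatability is checked at Visits 2 and 3.

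The one test described as symptom-limited is the incremental test at Visit 1, before any study drug.

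**The concern.** A reason for stopping is a natural outcome when the patient decides when the test ends. Here the protocol sets the end of the test, and the load is selected in advance so that the patient gets there. For a completer, the question of why exercise stopped has one true answer: the 4 minutes were over. The planned comparison therefore pools two kinds of answer, those from patients who were limited and those from patients who were not.

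What is at stake is how a secondary table is read. In a trial about mechanisms of dyspnea relief, a statement that fewer patients stopped because of breathlessness on one drug is attractive. It would mislead if most of those patients had completed the test.

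**Working it through.** **The plan's own figure.** The documents give no figure for stopping reasons. The only stated figure is the sample size: 17 patients, a difference of 1 Borg unit, SD of the within-patient difference 1.35, two-sided alpha 0.05. For a paired t-test the noncentrality is (1/1.35) × √17 = 3.05. The noncentral t gives 81.8% power at n=17 and 79.1% at n=16, so 17 is reproduced. The point below does not depend on it.

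**Step 1: which tests can supply the comparison.** Only tests after study drug can differ by treatment. There is one per patient at each of Visits 4 and 5, so 17 per treatment and 34 in all. The Visit 1 incremental test cannot contribute.

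**Step 2: what each test can tell.** If the patient completes, the recorded reason is either the residual category (time elapsed) or a symptom that did not end the test. If the patient stops early, the reason is a real limitation outcome. Nothing in the documents restricts the analysis to early stops. If all 34 tests were completed, none would be symptom-limited. That is an assumption about completion, not a figure in the plan.

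**Step 3: how many early stops Fisher's test would need.** With k early stops of 17 on one treatment and none on the other, the two-sided p-value is 2 × C(17,k) / C(34,k).

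- k=4: 2 × 2,380 / 46,376 = 0.103
- k=5: 2 × 6,188 / 278,256 = 0.044

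So at least 5 against 0 is needed. The same arithmetic shows the risk of misreading. If everyone completed, and 5 of 17 named breathing after one drug and none after the other, Fisher's test would also give p=0.044, although no symptom had ended any test.

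**Step 4: effect of pairing.** Both post-drug tests come from the same patient. With k discordant pairs all in one direction, exact McNemar gives 2 × 0.5^k: 0.0625 for k=5 and 0.031 for k=6. The 5-against-0 result that Fisher's test calls significant is not significant in the paired analysis.

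**Step 5: chance of a significant Fisher result.** The early-stop rates are assumed, and the two treatments are treated as independent. Expected early stops are 17 × (p1 + p2).

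| Early-stop rates | Expected early stops of 34 | Chance of p<0.05 |
|---|---|---|
| 5% vs 5% | 1.7 | 0.1% |
| 5% vs 10% | 2.6 | 1.0% |
| 5% vs 20% | 4.3 | 11.6% |
| 10% vs 30% | 6.8 | 18.6% |
| 0% vs 30% | 5.1 | 61.1% |

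At the low rates that the load selection aims for, the comparison carries almost no information on limitation.

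**Step 6: between-groups.** The *Subjects* section describes one population of 17, and the design is a two-treatment crossover. No grouping factor is named for this comparison.

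**The case against.** The strongest reply is that the load is the highest the patient can sustain, and may be raised to 90%, so patients work near their limit. Some may stop early at Visits 4 and 5, and for them the reason is a genuine symptom outcome. This stands. A reader might infer that the planned outcome reflects only the clock and never a symptom, but the documents do not support that. They neither rule out early stops nor exclude patients who have them.

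Second, patients state their reason in their own words and a residual category exists, so a completer can truthfully say that time was up. If all completers did so, the planned frequency table would already show early stops and their reasons. This also stands. A reader might conclude that any reported treatment difference in stopping reasons would be false. That follows only if completers name a symptom and the report presents it as having stopped them. The documents neither ensure nor prevent this, because completion is not a recorded category.

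Third, low power is usual for a descriptive frequency at n=17, and the rates in the table are assumptions. Agreed: the table shows how little information to expect and does not itself show invalidity. The misfit between question and design does not depend on it.

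Fourth, treatment order is randomized, so two order groups exist. The analysis section does not say that these are meant, so the term is undefined rather than shown to be empty.

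**Conclusion.** The point holds in a limited form. The plan applies a between-treatment test to reasons for stopping, while the only post-drug tests have a fixed duration and a load selected for completion. Answers from completers say nothing about limitation; answers from early stoppers do, and the plan does not separate the two. The named test also ignores within-patient pairing, and one of the two stated comparisons has no defined referent.

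The size is small: one secondary descriptive outcome. Stopping reasons appear in neither the objective, the hypothesis nor the sample-size basis. It would be wrong to extend the point to the primary endpoint, the change in dyspnea at 4 minutes, which a fixed duration suits well. The end-exercise dyspnea descriptors in the same sentence also remain meaningful at a fixed time.

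The conclusion rests on the documented design. Only the numerical illustration rests on assumed early-stop rates.

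**What to change.** 1. In *Symptom evaluation*, add completion of the 4 minutes as its own category, and keep the symptom reasons for tests that end early.
2. In *Statistical analysis*, remove the between-treatment Fisher test of stopping reasons. Report instead, by treatment and paired within patient, the number of post-drug 4-minute tests not completed, with the reason for each. If a test is wanted, use exact McNemar on completion.
3. Delete the between-groups wording, or say which groups are meant.

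No new question is needed. The relative weight of dyspnea and leg discomfort under each treatment is already available from the Borg ratings at 4 minutes.

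The cost is one revised analysis sentence and one category on the form, with no added visits or measurements. The downside is the loss of one categorical comparison.
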